10 MANAGEMENT OF SUBJECTS

10.1 Notification to Other Departments and Hospitals

Prior to the start of study drug administration, the investigator or subinvestigator will check whether the subject is visiting other departments or hospitals. If the subject has been visiting another department or hospital, the investigator or subinvestigator will inform the attending physician of the subject's participation in the study. If subjects used a drug other than those prescribed by the investigator or subinvestigator, the name and use status of the drug will be investigated.

The investigator or subinvestigator will take a similar action if a subject has newly visited another department or hospital during the study period.

10.2 Subject Compliance Instruction and Investigation of Compliance Status

The investigator or subinvestigator will prescribe the study drug to the subject at each visit. When prescribing the study drug, each subject will be explained and instructed on the dosage and administration and how to take the drug. As a guide, subjects will be instructed to take the drug once daily at 24-hour intervals, twice daily at 12-hour intervals, three times daily at 8-hour intervals, or four times daily at 6-hour intervals. Subjects will be instructed to bring at the next visit the study drugs that were not taken and empty PTP sheets for study drugs that were taken. If non-compliance with the study drug is noted, thorough instructions will be given once again. In particular, if an overdose is observed, the investigator or subinvestigator will take adequate measures while giving due consideration to the safety of the subject and determine whether or not the subject may continue the study.

10.3 Instructions to Subjects

The investigator, subinvestigator, or clinical study collaborator will instruct subjects on the following.

10.3.1 Visits to the Hospital

After giving their written informed consent, subjects will undergo screening. Afterwards, subjects will visit the hospital in accordance with Section 9.1 "Schedule." Subjects who have been withdrawn from the study will undergo withdrawal examination as soon as possible.

10.3.2 Medication Diary

The investigator or subinvestigator will explain and instruct subjects to describe in the medication diary the status of study drug compliance on a daily basis and the time when the study drug was last taken before the scheduled visit, after the start of study drug administration. Subjects will also be instructed to bring their medication diary with them on scheduled visit dates. The medication diary will be checked on each scheduled visit date as to whether the medication diary is kept as specified in Section 10.2 "Subject Compliance Instruction and Investigation of Compliance Status." If any inappropriate description is found, instructions will be given once again.

10.3.3 Contraception

The investigator or subinvestigator will instruct the subject to use appropriate contraceptive methods from the date of informed consent until 12 weeks after the end of the study drug administration in females

of childbearing potential or from the date of the start of the study drug administration until 12 weeks after the end of the study drug administration in men of reproductive potential. The appropriate contraceptive methods are either a combination of two types from among condoms, oral contraceptives, intrauterine contraceptive devices, and diaphragms, or abstinence. The investigator or subinvestigator will adequately inform subjects about the risk of pregnancy and the appropriate contraceptive methods.

10.3.4 Measures Taken in the Event of Pregnancy

Female subjects will be instructed to promptly report to the investigator or subinvestigator if it is found that they are pregnant after informed consent, and male subjects will also be instructed to promptly report to the investigator or subinvestigator if their partner becomes pregnant after the start of study drug administration. In the event that a female subject becomes pregnant, the investigator or subinvestigator will take appropriate measures for safety assurance, such as immediately withdrawing the subject from the study, and will follow up the subject until follow-up is deemed no longer necessary. In the event that a partner of a male subject becomes pregnant, the necessary follow-up and other measures will be performed after obtaining voluntary written consent of the partner.

11 ADVERSE EVENT REPORTING

11.1 Adverse Events for Mandatory Reporting

11.1.1 Definition of Serious Adverse Events

See Section 9.5.2 “Definition of Serious Adverse Events.”

11.1.2 Treatment and Follow-Up of Adverse Events

11.1.2.1 Treatment of the Subject

If an adverse event occurs, the investigator or subinvestigator will take appropriate measures to ensure the safety of the subject, such as providing appropriate medical care or withdrawing the subject from the study as necessary.

11.1.2.2 Reporting to the Parties Concerned

11.1.2.2.1 Reporting of Serious Adverse Events

- 1) If a serious adverse event occurs, the investigator or subinvestigator will immediately (within 24 hours of learning of the event’s occurrence) report the event to the Emergency Safety Information Reception Center or the sponsor, either orally, by telephone, email, or fax (using Attachment 4 “Serious Adverse Event Report (First Report)” of the protocol (supplementary volume) or in the form specified by the study site), regardless of whether the event is causally related to the administration of the study drug.
- 2) Afterwards, the investigator will also submit a Serious Adverse Event Report (Detailed Report) to the sponsor and the head of the study site within 7 days after he/she becomes aware the event’s occurrence. In doing so, the investigator will report to the head of the study site by identifying any serious unexpected adverse drug reaction.
- 3) The investigator will also provide additional information as requested by the sponsor, the head of the study site, and the IRB.
- 4) The head of the study site will consult the IRB as to whether the study may be continued at the study site.

Emergency contact

Emergency Safety Information Reception Center

Tel.: (pronounced as “*shikyu fukusayo*” in Japanese, meaning urgency and adverse drug reaction); fax:
Reception hours: 24 hours (seven days a week)

11.1.2.2.2 Reporting of Non-Serious Adverse Events

If any adverse event of special concern occurs, the investigator or subinvestigator will promptly report to the sponsor about the event and the measures taken. Any other adverse events will also be reported to the sponsor as appropriate.

11.1.2.3 Follow-Up of Adverse Events

Adverse events will be followed until they have been reversed to their state before study drug administration, or until the investigator or subinvestigator determines that follow-up is no longer necessary based on the subject's condition, including symptoms, findings, and laboratory values. The eCRF should include information from study drug administration to the end of the study.

12 CRITERIA FOR SUBJECT WITHDRAWAL AND DISCONTINUATION OF THE STUDY, AND PROCEDURES THEREFOR

12.1 Withdrawal of a Subject from the Study

12.1.1 Subject Withdrawal Criteria

A subject will be withdrawn from the study if any of the following conditions apply.

- 1) The subject is found to be ineligible for participation in this study after the start of the study.
- 2) The subject wishes to withdraw the consent for the study.
- 3) It is found not feasible to conduct the necessary observations and examinations due to the subject's private reasons.
- 4) The subject experiences an adverse event, and the investigator or subinvestigator determines that the subject should be withdrawn from the study.
- 5) The subject applied PTx or parathyroid intervention therapy.
- 6) The subject has not taken investigational therapy over 8 weeks.
- 7) The investigator or subinvestigator determines that the subject should be withdrawn from the study.

12.1.2 Procedure for Withdrawing Subjects

The investigator or subinvestigator will take appropriate measures for a subject who has been withdrawn from the study due to a safety problem such as the occurrence of an adverse event. All subjects who have been withdrawn from the study will undergo withdrawal examination as soon as possible after safety is confirmed.

For subjects who stopped visiting the hospital after study drug administration, follow-up and prespecified assessments will be carried out as much as possible while taking into account the human rights of the subject.

The investigator or subinvestigator will investigate the date of withdrawn and the reason for withdrawal, and enter this information into the eCRF.

12.2 Site-Specific Study Discontinuation or Interruption

In the event of discontinuation or interruption of the study at a given study site due to reasons such as doubts about the safety of the study drug, the investigator must promptly notify the head of the study site in writing and provide a detailed written explanation of the discontinuation or interruption. The head of the study site will promptly report to the sponsor and IRB in writing to that effect and the reasons therefor.

This study will also be discontinued at the study site if any of the following conditions apply. In that case, appropriate measures will be taken in the same manner as above.

- 1) The head of the study site proposes the revision of the protocol based on the opinions from the IRB that the head of the study site consulted, but the sponsor cannot accept the proposal.
- 2) The IRB consulted by the head of the study site states that the study should not be continued, and the head of the study site directs that the study be discontinued.
- 3) The study site has committed a serious or continuing violation of GCP, this protocol, or the clinical study agreement.

12.3 Discontinuation or Suspension of the Entire Study

In the event of discontinuation or suspension of the entire study during the course of the study, the sponsor will promptly notify the head of all study sites and the regulatory authorities, providing them with the details of the reasons for the discontinuation or suspension. Upon receiving the notification, the head of the study site will promptly notify the investigator and the IRB of the discontinuation or suspension and the reasons therefor in writing. If the entire study is discontinued or suspended, the investigator will promptly notify subjects of the discontinuation or suspension, provide appropriate medical care, and take other necessary measures.

13 STATISTICAL ANALYSIS

13.1 Statistical Analysis Methods

The main analytical items for evaluation of efficacy, safety, and pharmacokinetics, as well as the analytical methods, are as follows.

Unless otherwise noted, categorical data will be summarized by frequency and percentage, and continuous data by summary statistics. The summary statistics will involve calculation of the number of subjects, mean, standard deviation, minimum, median, and maximum.

13.1.1 Efficacy Evaluation

13.1.1.1 Primary Evaluation

- The number and percentage of subjects whose corrected serum Ca level was maintained at ≤ 10.3 mg/dL for 2 weeks in the evaluation period will be calculated, along with the exact 95% confidence interval. Whether or not the lower limit of the exact 95% confidence interval exceeds the threshold ratio of 11% will be used as a criterion for judging the efficacy.

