4 STUDY DESIGN

4.1 Study Design

[figure not shown]
The design of this study is outlined in Table 4.1-1.

This study is a multicenter, intra-subject dose adjustment study. It consists of the screening period (from the time of consent to the start of study drug administration), the evaluation period (up to 24 weeks from the start of study drug administration), and the extended administration period (until Week 52 after the evaluation period).

The investigator or subinvestigator will conduct the screening after obtaining the written consent.

Subsequently, eligible subjects will be enrolled before the start of study drug administration.

Table 4.1-1. Outline of the study design

After enrollment, the date of the start of study treatment (Day 1) will be defined as Week 0, and the subjects will start to receive study drug at the starting dose of 2 mg once daily (daily dose: 2 mg). However, the starting dose may be 2 mg twice daily (daily dose: 4 mg) for subjects with a corrected serum Ca level of > 12.5 mg/dL at screening. Subsequently, the dose level will be adjusted for each subject in accordance with Section 7.1.1 "Dose, Mode of Administration, and Dosing Period" so that corrected serum Ca level can be controlled at ≤ 10.3 mg/dL, and the study drug will be orally administered at each dose level 1 to 4 times daily.

Subjects whose corrected serum Ca level have been maintained at ≤ 10.3 mg/dL for 2 weeks will be transferred to the extended administration period at the time even before Week 24. Other subjects will be transferred to the extended administration period at Week 24 if the investigator or subinvestigator has confirmed that there are no problems with their transfer to the extended administration period. See Table 9.1-1 "Schedule of observation, investigation, and examination (evaluation period)" and Table 9.1-2 "Schedule of observation, investigation, and examination (extended administration period)" for visit schedules for subjects transitioning to the extended administration period before Week 24. The study treatment period will be 52 weeks consisting of the evaluation period and the extended administration period. The time of transition to the extended administration period (starting week of prolongation) will be recorded in the electronic case report form (eCRF). Subjects will be withdrawn from the study at the end of the evaluation period if, at the discretion of the investigator or subinvestigator, they will not be transferred

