to the extended administration period. If a subject did not enter the extended administration period, the reason will be recorded in the eCRF.

Subjects will visit the hospital once every 2 weeks during the evaluation period. In the extended administration period following the evaluation period, subjects should visit the hospital to undergo scheduled tests at Weeks 8, 12, 16, 20, 24, 28, 32, 36, 40, 44, 48, and 52. If the dose is increased or administration is resumed after an interruption, the date 2 weeks after the dose increase or resumption will be designated as the date of post-dose-increase (or post-resumption) visit, on which the subject should visit the hospital to undergo scheduled tests.

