7.1.1.2.4 Criteria for Treatment Interruption

Study drug administration will be interrupted if any of the following criteria is met.

- Corrected serum Ca level ≤ 7.5 mg/dL.
- The investigator or subinvestigator has determined that study drug administration should be interrupted due to the occurrence of an adverse event, etc.
- The investigator or subinvestigator has determined that the dose should be reduced while the study drug is administered at a dose of 2 mg once daily (daily dose: 2 mg).

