7.1.1.2.5 Resumption of Study Drug Administration After Interruption

In principle, study drug administration will be resumed on the day of scheduled visit. Administration will be resumed after the corrected serum Ca level has reached or exceeded 8.4 mg/dL AND the investigator or subinvestigator has judged that administration can be resumed in consideration of the safety of the subject. The dosage and administration at the time of resumption of administration will be the same as those immediately before interruption or the dosage and administration at a lower level.

The duration of an interruption should not exceed 8 consecutive weeks; if the investigator or subinvestigator has judged that it is impossible to resume administration, the subject will be withdrawn from the study.

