9 OBSERVATION, INVESTIGATION, AND EXAMINATION ITEMS AND SCHEDULE

9.1 Schedule

Screening will be performed in subjects who have given their written informed consent. Afterwards, the study drug will be administered to subjects whose eligibility has been confirmed and for whom registration has been completed, and observation, investigation, and examination will be performed according to the schedule described in Table 9.1-1 and Table 9.1-2. Details are given in Section 9.3 “Observation and Investigation Items and the Timing Thereof” and Section 9.4 “Examination Items and the Timing Thereof.” Visits and examinations will be carried out on the scheduled visit dates with an allowable window of ± 4 days during the period between Week 2 and Week 24, and on the scheduled visit dates with an allowable window of ± 7 days thereafter. If a decision is made to discontinue study drug administration on a day of scheduled visit, the results of the examination on that scheduled visit date may be handled as the results of withdrawal examination.

Table 9.1-1. Observation, investigation, and examination schedule (evaluation period)

	Obtaining informed consent	Screening	Registration	Evaluation period														1 At discontinuation
				Time after administration of the study drug (Weeks)														
				0	2	4 ^e	6 ^e	8 ^f	10 ^f	12 ^g	14 ^g	16 ^h	18 ^h	20 ⁱ	22 ⁱ	24 ^j		
Time after administration (h)				Before administration	0.5	1	2	3										
Obtaining informed consent	X																	
Study drug administration					←												→	
Subject demographics	X ^a																	
Registration		X																
Height	X ^a																	
Body weight				X														X X
QOL assessment				X														X X
Vital sign				X				X X	X X	X X	X X	X X	X X	X X	X X	X X	X X	
Hematology				X				X X	X X	X X	X X	X X	X X	X X	X X	X X	X X	
Blood biochemistry 1	X ^b			X				X X	X X	X X	X X	X X	X X	X X	X X	X X	X X	
Blood biochemistry 2				X				X X	X X	X X	X X	X X	X X	X X	X X	X X	X X	
Urinalysis				X				X X	X X	X X	X X	X X	X X	X X	X X	X X	X X	
Plasma drug concentration ^c				X X X X	X X ^k			X ^k		X ^k		X ^k		X ^k		X ^k		
Pregnancy test ^d	X																	X
Electrocardiogram (12-lead)				X				X X	X X	X X	X X	X X	X X	X X	X X	X X	X X	
Adverse events					←												→	
Confirmation of the use status of concomitant medications	←																	→
Investigation of administration status					←												→	

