The allowable window period is ± 4 days of the scheduled visit dates (except for Week 0).

a) Performed after informed consent is obtained and before the start of study drug administration (Week 0).

b) Corrected serum Ca, Ca, and Alb levels will be measured. In the event that the test result does not meet inclusion criteria 4), re-testing may be performed. If performed in Week 0, it will be handled as a test result in Week 0.

c) From Week 2 onwards, if a subject is not taking the study drug as of the day before his/her visit to the hospital, it is permissible not to perform blood collection on the day of hospital visit. It is also permissible not to perform post-dose blood collection in a subject for whom a decision to interrupt study drug administration has been made on the day of hospital visit.

d) Female subjects only. However, no pregnancy test is required if at least 12 months have passed since the last menstrual period without any other medical reason.

e) Subjects whose corrected serum Ca level has been maintained at ≤ 10.3 mg/dL for 2 weeks will immediately transition to the extended administration period, with the next visit being Week 8.

f) Subjects whose corrected serum Ca level has been maintained at ≤ 10.3 mg/dL for 2 weeks will immediately transition to the extended administration period, with the next visit being Week 12.

g) Subjects whose corrected serum Ca level has been maintained at ≤ 10.3 mg/dL for 2 weeks will immediately transition to the extended administration period, with the next visit being Week 16.

h) Subjects whose corrected serum Ca level has been maintained at ≤ 10.3 mg/dL for 2 weeks will immediately transition to the extended administration period, with the next visit being Week 20.

i) Subjects whose corrected serum Ca level has been maintained at ≤ 10.3 mg/dL for 2 weeks will immediately transition to the extended administration period, with the next visit being Week 24.
 j) Subjects whose corrected serum Ca level has been maintained at ≤ 10.3 mg/dL for 2 weeks will immediately transition to the extended administration period, with the next visit being Week 28.
 k) If the subject transitions to the extended administration period, plasma drug concentrations may be measured at the end of the evaluation period (0.5, 1, 2, and 3 hours) (see Table 9.1-2 "Observation, investigation, and examination schedule (extended administration period)").

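### Calcium values taken while KHK7580 is interrupted can count towards response and can trigger early transfer to a sparser visit schedule

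*Combined protocol and SAP*

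**What the plan says.** All references are to the combined protocol and SAP.

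- **Response.** Section 13.1.1.1 calculates "The number and percentage of subjects whose corrected serum Ca level was maintained at ≤ 10.3 mg/dL for 2 weeks in the evaluation period" and judges efficacy by whether the exact 95% lower limit exceeds 11%. The FAS (13.7.1) requires some study drug and some calcium value after the start of treatment, and nothing about adherence.
- **Interruption.** Section 7.1.1.2.4 stops the drug at "Corrected serum Ca level ≤ 7.5 mg/dL", for an adverse event, or when a reduction is needed at the lowest dose. On restarting, Section 7.1.1.2.5 says "Administration will be resumed after the corrected serum Ca level has reached or exceeded 8.4 mg/dL", subject also to the investigator's judgment. It adds: "The duration of an interruption should not exceed 8 consecutive weeks".
- **Visits.** Section 4.1: "Subjects will visit the hospital once every 2 weeks during the evaluation period". No exception is made for interrupted subjects. Note c of Table 9.1-1 lets a subject who is not taking drug skip the plasma drug sample, but waives no calcium test.
- **Early transfer.** Section 4.1 and notes e to i use the same calcium condition. Under note g such subjects "will immediately transition to the extended administration period, with the next visit being Week 16". The investigator's check applies only to the remaining subjects, who transfer "at Week 24 if the investigator or subinvestigator has confirmed that there are no problems with their transfer".
- **Missing data.** Section 13.5 classes a subject without evaluable data for two consecutive weeks as not achieving response. It does not define evaluable or link it to dosing.

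**The concern.** The primary objective is the efficacy of KHK7580 given by mouth, tested in one arm against a fixed threshold. A calcium value taken after the drug was stopped is weak evidence that the drug held calcium down for 2 weeks, yet nothing in the public text separates it from a value on treatment. The secondary endpoint of a fall of at least 1.0 mg/dL has the same feature.

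The same calcium condition also changes care. A subject whose drug is being withheld for safety can be moved from 2-weekly visits to the 4-weekly schedule without the check that Section 4.1 asks for in other subjects. The extra visit 2 weeks after resumption does not help someone who has not resumed. Further safety tests are allowed (9.6) but not scheduled.

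Two things are at stake: one or more classifications in a very small trial, and the spacing of calcium checks in a few subjects.

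**Working it through.** **1. Can an off-drug value complete a response?** Calcium is tested every 2 weeks, an interruption may last 8 weeks, and the rule looks only at calcium. Example: calcium is above 10.3 at Week 8 and at or below 10.3 at Week 10, when drug is stopped for an adverse event. It is still at or below 10.3 at Week 12. As written, this is a response, transfer follows at Week 12, and the next scheduled visit is Week 16.

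**2. How does the low-calcium route compare?** If the visit before the value of 7.5 or less was already at or below 10.3 on drug, those two visits form a response on treatment. A response that needs an off-drug value therefore requires a drop from above 10.3 to 7.5 or less between consecutive visits, that is by more than 10.3 − 7.5 = 2.8 mg/dL. That is narrow. The adverse-event route in step 1 needs no such drop.

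Transfer is a separate matter. With calcium above 10.3 at Week 8, 10.0 at Week 10 and 7.4 at Week 12, the response is on drug. The subject must nevertheless be interrupted and transferred at the same visit, with the next scheduled visit at Week 16.

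**3. Visit spacing.** Early transfer can occur at 10 visits (Weeks 4 to 22). At Weeks 4, 8, 12, 16 and 20 the next scheduled calcium is 4 weeks away instead of 2. At Weeks 6, 10, 14, 18 and 22 it remains 2 weeks away. Section 9.1 says "Visits and examinations will be carried out on the scheduled visit dates with an allowable window of ± 4 days" for Weeks 2 to 24. A 4-week gap can thus run from 28 − 8 = 20 to 28 + 8 = 36 days, against 14 − 8 = 6 to 14 + 8 = 22 days for a 2-week gap.

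**4. Decision rule.** The only sizing inputs in the public text are a target of at least 10 treated subjects (13.2) and the 11% threshold (13.1.1.1). The expected rate and power belong to Section 24.10, whose content is not shown, so there is no planned power to reproduce. The exact lower limit for x responders among n is the 2.5% quantile of Beta(x, n − x + 1).

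| n | Responders | Lower limit | Exceeds 11%? |
|---|---|---|---|
| 10 | 3 | 6.67% | no |
| 10 | 4 | 12.16% | yes |
| 15 | 4 | 7.79% | no |
| 15 | 5 | 11.82% | yes |
| 18 | 5 | 9.69% | no |
| 18 | 6 | 13.34% | yes |

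One reclassified subject at the boundary changes the conclusion at each size shown.

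**5. Expected effect, under an assumption.** No interruption rate is given. Suppose off-drug values add q to each subject's chance of being called a responder. With n = 10, the chance of passing is P(X ≥ 4) for X binomial with probability p + q, where p is the true on-drug rate.

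| p | q = 0 | q = 1 point | q = 2 points | q = 5 points |
|---|---|---|---|---|
| 11% | 1.78% | 2.39% | 3.13% | 6.14% |
| 30% | 35.04% | 37.72% | 40.44% | 48.62% |
| 50% | 82.81% | 84.40% | 85.90% | 89.80% |

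The chance of at least one such subject among 10 is 1 − (1 − q)^10 = 9.6%, 18.3% or 40.1% for q = 1, 2 or 5 points.

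**The case against.** Several objections carry weight.

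- **Estimand.** Interruption and resumption sit within the dose adjustment criteria (7.1.1.2), so they are part of the regimen under test. Counting calcium whatever the interruption status is a legitimate strategy. This stands, and it is why that analysis should be kept. What is missing is a stated choice.
- **Direction of bias.** Calcium would be expected to rise off drug, so many such pairs will fail on their own. Cinacalcet is prohibited (7.2.1), changes in other calcium-active drugs are barred (7.2.2), and parathyroid surgery or intervention leads to withdrawal (12.1.1). A value still at or below 10.3 soon after stopping may be residual drug effect. This stands and limits the size of the concern.
- **Silence.** The documents never say that off-drug values count. Section 13.6 leaves details to an analysis plan finalised by database lock. Neither that plan nor the Section 24.8 rationale is in the public text, and either might settle the matter. This stands for the analysis. It does not help transfer, which is a matter of protocol conduct.
- **Monitoring.** Sections 14.2 and 11.1.2.1 oblige investigators to watch and treat subjects, and the plan accepts 4-weekly visits for interruptions arising later in the extension. A reader might infer that interrupted subjects go unmonitored. The text does not support that; what is lost is a scheduled calcium test that the evaluation period already provides.

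A reader might also infer that the responder rule needs a lower calcium limit. The documents do not make that a defect: the endpoint concerns control of hypercalcaemia, and low calcium on treatment is handled separately by the interruption rule.

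**Conclusion.** The concern holds in a limited form. As worded, both the responder rule and the early-transfer rule depend on calcium alone, so an interrupted subject can be counted as a responder and can move to the extension with the next scheduled calcium up to 4 weeks away.

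The expected effect on the primary result is small. At an assumed 1 added point the false-pass chance is 2.39%, still under 2.5%; at 2 points it is 3.13%. These increments are assumptions, and nothing in the documents supports a value as high as 5 points. It would be wrong to conclude that the primary result is biased upwards by a known amount or that the trial is invalid.

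The reason to act is that one subject can decide the result at n = 10 (6.67% against 12.16%, around 11%). Settling that subject's status as late as database lock, in a single-arm study with known dosing, would look post hoc. The change to transfer is justified separately, since it only keeps visits that are already planned.

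**What to change.** 1. **Transfer (Section 4.1; Table 9.1-1, notes e to i).** No subject transfers early while an interruption is in progress or is decided at that visit, whatever the calcium values. The subject stays on 2-weekly visits until drug is resumed or Week 24.
2. **Analysis (13.1.1.1, 13.1.1.2 and 13.5).** For both responder endpoints, the primary analysis requires no interruption or end of treatment at any time between the two qualifying samples. A sample on the day interruption is decided may serve as the second value. This also excludes an interruption that opens and closes between visits. A subject can still qualify after resuming. As a sensitivity analysis, count all calcium values before parathyroidectomy or parathyroid intervention, regardless of interruption.
3. **Listing.** For each responder, show the two qualifying dates, the calcium values, the dose and the interruption status.

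**Cost.** Item 1 is a short protocol amendment, needing investigator agreement and prior IRB review (16.3). Treatment start and end dates and the reasons for interruption are already collected (9.3.1), so items 2 and 3 need no new data. A briefly interrupted subject may lose one qualifying pair; the sensitivity analysis shows the effect.
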